5.6.1.2 QTc prolongation

In light of the potential for QT changes associated with osimertinib, electrolyte abnormalities (hypokalemia, hypomagnesaemia, hypocalcemia) must be corrected to be within normal ranges prior to first dose and electrolyte levels monitored during study treatment.

Patients with QTcF prolongation to >500 msec should have study treatment interrupted and regular ECGs performed until resolution to <481 msec or recovery to baseline if baseline QTcF is >481 msec and then restarted at a reduced dose of 40 mg, or 80mg at the discretion of the investigator. If the toxicity does not resolve to \leq grade 1 within 21 days of withholding osimertinib the patient will be permanently withdrawn from study treatment.

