5.6.1 Osimertinib

All patients start treatment with osimertinib at 80 mg daily irrespective if the patient received osimertinib as first-line treatment or as sequential treatment after gefitinib. Only 1 dose reduction with osimertinib (to 40 mg) will be allowed during the study.

If a patient experiences a CTCAE grade 3 or higher and/or unacceptable toxicity (any grade) not attributable to the disease or disease-related processes under investigation, where the Investigator considers the AE of concern to be specifically associated with the study drug dosing will be interrupted and supportive therapy administered as required in accordance with local practice/guidelines.

If the toxicity resolves or reverts to ≤CTCAE grade 2 within 3 weeks of onset, study drug may be restarted at the same dose (starting dose) or a lower dose (40 mg) using the rules below for dose modification (Table "Recommended dose modifications with osimertinib). There will be no individual modifications to dosing schedule in response to toxicity, only potential dose reduction or dose interruption. If restarting at the same dose level, patients should be closely monitored for 3 days following the restart of treatment. If within 3 days there is recurrence of same toxicity, a dose reduction should be considered at the Investigator's discretion.

If the toxicity does not resolve to ≤CTCAE grade 2 after 3 weeks of withholding osimertinib, then the patient should be withdrawn from the study treatment and observed until resolution of the toxicity. There will be no individual modifications to treatment schedule in response to toxicity, only potential dose reduction or dose interruption.

If an AE subsequently requires dose interruption, study drug may restart at the same dose or the reduced dose, on resolution/improvement of the AE at the discretion of the investigator as described above.

Recommended dose modifications with osimertinib

Target Organ	Adverse reaction	Modification
Pulmonary	Interstitial lung disease (ILD)/Pneumonitis	Permanently discontinue osimertinib
Cardiac	QTc† interval greater than 500 msec on at least 2 separate ECGsb	Withhold osimertinib until QTc interval is less than 481 msec or recovery to baseline if baseline QTc is greater than or equal to 481 msec within 3 weeks of withholding osimertinib, then resume at 40 mg dose or at 80 mg (at the discretion of the investigator, to allow for situations where causality in relation to osimertinib may be difficult to determine)

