	QTc interval prolongation with signs/symptoms of serious arrhythmia	Permanently discontinue osimertinib
	Asymptomatic, absolute decrease in LVEFc of 10% from baseline and below 50%	 Withhold osimertinib for up to 2 weeks. If improved to baseline LVEF, resume. If not improved to baseline, permanently discontinue.
	Symptomatic congestive heart failure	Permanently discontinue osimertinib
Other	Grade 3 or higher adverse reaction	Withhold osimertinib for up to 3 weeks
	If improvement to Grade 1 within 3 weeks	Resume at 80 mg or 40 mg daily
	If no improvement to Grade1 within 3 weeks	Permanently discontinue osimertinib

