5.7.4 Other concomitant therapies

In case of RECIST 1.1 progression on a known lesion during osimertinib treatment, surgery, radiotherapy and cryotherapy will be allowed.

No other systemic anticancer therapies will be allowed.

Administration of Covid vaccine will be a treating physician decision after evaluation of benefit-risk ratio and depending of local vaccine availability and compliance with local regulatory guidelines. In cancer patients, the use of inactivated virus vaccines are usually permitted and live vaccines are generally prohibited in those receiving immunosuppressive treatments. Information on the mRNA based COVID-19 vaccines when used in cancer patients is currently not available. See Appendix F for EMA recommendations.

6 Clinical evaluation, laboratory tests and follow-up

As described in chapter 4, a cycle of treatment is defined as 28 days of once daily treatment with osimertinib or gefitinib.

In arm A, after 24 weeks, the duration between study visits will change from every 28 days (4 weeks) to every 56 days (8 weeks).

In arm B and C, study visits will be every 28 days (4 weeks) until the switch to osimertinib. After that, one visit will be performed 28 days after osimertinib initiation, the second one at 8 weeks with radiological evaluation and then every 56 days (8 weeks) if no progression on the first CT scan after osimertinib initiation.

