6.2.3.1 Day 1 cycle 1 (within 3 days prior to actual osimertinib dosing)

- Adverse events and Performance Status assessment;
- Physical examination, including vital signs, height, weight and blood pressure;
- Collection of concomitant medication;
- Laboratory examination including:
 - hematology: please see section 6.1.1;
 - biochemistry: please see section 6.1.1.
- Digital ECG with QT interval;
- LVEF assessed by MUGA or ECHO
- Ophthalmological examination.

6.2.3.2 Every 4 weeks (+/-2 days) from week 1 until week 24

- Adverse events and Performance Status assessment;
- Collection of concomitant medication;
- Physical examination, including vital signs, height, weight and blood pressure;
- Laboratory examination including:
 - hematology: please see section 6.1.1;
 - biochemistry: please see section 6.1.1.
- Digital ECG with QT interval;
- Ophthalmological examination if clinically indicated.

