6.3.3.1 Day 1 cycle 1 (within 3 days prior to actual osimertinib dosing)

- Adverse events and Performance Status assessment;
- Physical examination, including vital signs, height, weight and blood pressure;
- Collection of concomitant medication
- Laboratory examination including:
 - hematology: please see section 6.1.1;
 - biochemistry: please see section 6.1.1.
- Digital ECG with QT interval;
- LVEF assessed by MUGA or ECHO
- Ophthalmological examination.

6.3.3.2 Every 4 weeks (+/-2 days) from week 1 until week 24

- Adverse events and Performance Status assessment;
- Collection of concomitant medication;
- Physical examination, including vital signs, height, weight and blood pressure;
- Laboratory examination including:
 - hematology: please see section 6.1.1;
 - biochemistry: please see section 6.1.1.
- Digital ECG with QT interval;
- Ophthalmological examination if clinically indicated.

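### Sections 5.6.1 and 5.6.1.2 set different QTc triggers for interrupting osimertinib: a reading above 500 msec with no confirmation step, or such readings on two or more ECGs

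*Combined protocol and SAP*

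**What the plan says.** Two places in the protocol tell sites when to stop osimertinib for a prolonged QT interval.

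- Section 5.6.1.2, the subsection on QTc prolongation: "Patients with QTcF prolongation to >500 msec should have study treatment interrupted". It states no number of ECGs. The ECGs it goes on to mention come after the interruption and follow recovery.
- Section 5.6.1, QTc row of the table of recommended modifications: withhold when the QTc is "interval greater than 500 msec on at least 2 separate" ECGs.

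Three other statements in section 5.6.1 bear on the same patient.

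- A general rule covers toxicity of grade 3 or higher, or unacceptable toxicity of any grade, "where the Investigator considers the AE of concern to be specifically associated with the study drug dosing will be interrupted".
- A separate table row requires permanent discontinuation for "QTc interval prolongation with signs/symptoms of serious arrhythmia".
- The text introduces the table with the words "using the rules below for dose modification", in a sentence about the dose at which the drug may be restarted once toxicity has resolved.

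**The concern.** A rule for stopping a drug with a recognised QT risk should read the same wherever a site finds it. Here the answer to a simple question, whether one reading above 500 msec is enough to stop, depends on whether the investigator opens the table or the subsection. The protocol takes the risk seriously elsewhere: it excludes patients with a QTc above 470 msec at randomization (section 3.2), requires electrolytes to be corrected before the first dose (5.6.1.2), and gives long guidance on QT-prolonging drugs (Appendix E). All three arms are planned to receive osimertinib, arm A from the start and arms B and C after the switch, so the trigger applies across the trial.

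What is at stake is consistent safety management between sites, not the efficacy analysis.

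**Working it through.** No calculation applies. The check is to put the two triggers side by side and ask which patients they treat differently.

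| Patient on osimertinib | Section 5.6.1.2 | QTc row, 5.6.1 table |
|---|---|---|
| No reading above 500 msec | not met | not met |
| One ECG above 500 msec, no signs of serious arrhythmia | met: interrupt | not met |
| Two or more separate ECGs above 500 msec, no such signs | met: interrupt | met: withhold |
| Prolongation with signs or symptoms of serious arrhythmia | permanent discontinuation under the table's own row | same |

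Only the second line differs. The next step is to see whether another rule settles it.

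1. **General toxicity rule (5.6.1).** It applies where the investigator attributes the event to study drug, and the event must be grade 3 or higher or judged unacceptable. The documents do not reproduce the CTCAE grading of QTc, so they do not show whether a single reading qualifies by grade. The QTc row itself concedes that causality can be hard to establish. The rule permits stopping after one reading but leaves it to judgement.
2. **Arrhythmia row (5.6.1 table).** It removes patients with signs or symptoms and leaves those without.
3. **Precedence.** The introduction to the table concerns the restart dose. Section 5.5 cites section 5.6 and its subsections together, without ranking them, and only for permanent discontinuation. Neither says which interruption trigger governs.
4. **ECG practice.** Eligibility uses three ECGs (3.2). The on-treatment visits in 6.1.2.1, 6.2.3.2 and 6.3.3.2 list a digital ECG with no stated replicates. A lone reading above 500 msec is therefore a case sites could meet.

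The recovery rules were compared as well. Both places require QTc below 481 msec or return to a raised baseline, both allow three weeks (21 days), and both allow restart at 40 mg or 80 mg. They differ only at the margin: the table's baseline branch starts at 481 msec or more, that of 5.6.1.2 above 481 msec, and 5.6.1.2 adds a grade 1 criterion for permanent withdrawal. The disagreement that matters is confined to the trigger.

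**The case against.** The strongest reply is that both rules can be obeyed at once. The table says when to withhold; it never tells a site to continue after one reading. A site that follows 5.6.1.2 breaches nothing in the table, which is headed as recommendations. One could also treat the table as the fuller definition and 5.6.1.2 as shorthand for confirmed prolongation. The first argument stands in part: the two rules set different thresholds rather than opposite instructions, and harm requires a site to act on the table alone and not invoke the general rule. The second is a possible reading, but the protocol does not state it, and a reader could equally give priority to the dedicated subsection.

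Four stronger readings are tempting and are not supported.

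- **That the plan sets no time limit for the second ECG, or confuses QTc with QTcF.** The row carries footnote markers on exactly these two terms, and the footnote text is not in the available document. Section 3.2 also uses QTc for a machine-derived QTcF value. Neither can be called an omission.
- **That the table governs because section 5.6.1 sends sites to it.** That reference is about restarting, not interrupting.
- **That dosing could run on for 28 or 56 days until the next routine ECG.** These are nominal visit spacings. Nothing tells sites to wait for a scheduled visit, and an unscheduled repeat is not excluded, so the spacings do not measure time on drug.
- **That the trial's conclusions are at risk.** Nothing in the design or the primary analysis depends on this trigger.

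**Conclusion.** The inconsistency is real and limited. For a patient with a single reading above 500 msec and no signs of serious arrhythmia, section 5.6.1.2 interrupts osimertinib and the table's QTc row does not, and the available text does not say which prevails. The size is one reading against at least two. Frequency and clinical consequence cannot be estimated from the documents.

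The conclusion assumes that the missing footnotes do not resolve the matter. A footnote giving only a repeat interval or a correction formula would leave the conflict in place; one telling sites to hold dosing pending the repeat could remove it. The point is worth fixing because it concerns a stop-dosing rule and the correction is small.

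**What to change.** Check the table's footnotes in the full protocol first. If they do not settle the point, change the QTc row of the 5.6.1 table to match 5.6.1.2:

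- interrupt osimertinib at the first QTcF above 500 msec;
- repeat the ECG promptly;
- restart only once QTcF is below 481 msec, or back to baseline if baseline is 481 msec or more.

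The restart condition should be stated in those terms. Wording that allowed restart merely because the repeat failed to exceed 500 msec would admit values of 481 to 500 msec, which is looser than both sections now are. Using 481 msec or more for the baseline branch in both places removes the marginal mismatch. The restart doses and the three-week limit can stay as they are. The sponsor's medical team should confirm the choice.

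The cost is one table row, the small edit to the baseline branch in 5.6.1.2, and a letter to sites. For patients, it is an occasional brief interruption and a prompt repeat ECG for a reading that is not confirmed. If the repeat stays at 481 msec or above, the interruption lasts longer, as 5.6.1.2 already provides. No scheduled visits are added.

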5.6.1.3 Erythema multiforme and Stevens-Johnson syndrome

Case reports of Erythema multiforme (EM) and Stevens-Johnson syndrome (SJS) have been uncommonly and rarely reported, respectively, in association with osimertinib treatment. Before initiating treatment, patients should be advised of signs and symptoms of EM and SJS. If signs and symptoms suggestive of EM develop, close patient monitoring and drug interruption or discontinuation of osimertinib should be considered. If signs and symptoms suggestive of SJS appear, osimertinib should be interrupted or discontinued immediately.

5.6.1.4 Aplastic anaemia

Rare reports of aplastic anaemia have been reported in association with osimertinib treatment. Some cases had a fatal outcome. Before initiating treatment, patients should be advised of signs and symptoms of aplastic anaemia including but not limited to persistent fever, bruising, bleeding, and/or pallor. If signs and symptoms suggestive of aplastic anaemia develop, close patient monitoring and drug interruption or discontinuation of osimertinib should be considered. Osimertinib should be discontinued in patients with confirmed aplastic anaemia.

5.6.1.5 Changes in cardiac contractility

Based on the available clinical trial data, a causal relationship between effects on changes in cardiac contractility and osimertinib has not been established. In patients with cardiac risk factors and those with conditions that can affect LVEF, cardiac monitoring, including an assessment of LVEF at baseline and during treatment, should be considered. In patients who develop relevant cardiac signs/symptoms during treatment, cardiac monitoring including LVEF assessment should be considered.

5.6.1.6 Keratitis

Patients presenting with signs and symptoms suggestive of keratitis such as acute or worsening: eye inflammation, lacrimation, light sensitivity, blurred vision, eye pain and/or red eye should be referred promptly to an ophthalmology specialist.

5.6.2 Gefitinib

The initial dose for gefitinib (250 mg once daily) cannot be reduced to a lower dose. The dose of gefitinib may be withheld or discontinued if clinically indicated at the discretion of the Investigator

If a patient experiences a CTCAE grade 3 or higher and/or unacceptable toxicity (any grade) not attributable to the disease or disease-related processes under investigation, where the Investigator

considers the AE of concern to be specifically associated with the study drug dosing will be interrupted and optimal supportive therapy administered as required in accordance with local practice/guidelines.

If the toxicity resolves or reverts to CTCAE grade to baseline within 2 weeks of onset, study drug may be restarted at the same dose. If restarting at the same dose level, patients should be closely monitored for 3 days following the restart of treatment. If within 3 days there is recurrence of same toxicity patient should be withdrawn from the study treatment and observed until resolution of the toxicity.

For Grade 2 dermatological events, dosing may be continued at investigator discretion with optimal and appropriate supportive therapy administered as required in accordance with local practice / guidelines.

5.7 Concomitant treatments

5.7.1 Osimertinib

The use of any natural/herbal products or other "folk remedies" should be discouraged, but use of these products, as well as use of all vitamins, nutritional supplements, and all other concomitant medications must be recorded in the eCRF. In vitro data have shown that the principal CYP enzyme responsible for the Phase I metabolism of osimertinib is CYP3A4. Once enrolled all patients must try to avoid concomitant use of medications, herbal supplements and/or ingestion of foods that are known to be potent inducers of CYP3A4 whenever feasible, but patients may receive any medication that is clinically indicated for treatment of adverse events. Such drugs must have been discontinued for an appropriate period before they enter screening and for a period of 3 months after the last dose of osimertinib.

All concomitant medications should be captured on the eCRF. Guidance on medicines to avoid, medications that require close monitoring and on washout periods is provided (see Appendix E).

If medically feasible, patients taking regular medication, with the exception of potent inducers of CYP3A4 (see above), should be maintained on it throughout the study period. Patients taking concomitant medications whose disposition is dependent upon BCRP and which have a narrow therapeutic index should be closely monitored for signs of changed tolerability as a result of increased exposure of the concomitant medication whilst receiving osimertinib. Guidance on medications to avoid, medications that require close monitoring and on washout periods is provided (see Appendix E).

Patients taking rosuvastatin should have creatine phosphokinase levels monitored (due to BCRP mediated increase in exposure). If the patient experiences any potentially relevant AEs suggestive of muscle toxicity including unexplained muscle pain, tenderness, or weakness, particularly if accompanied by malaise or fever, rosuvastatin must be stopped and any appropriate further management should be taken.

Please refer to Appendix E for any further information on guidance for concomitant medications.

5.7.2 Gefitinib

Gefitinib is metabolized by the CYP3A4 and the CYP2D6.

Drugs which inhibit CYP3A4 activity (ketoconazole, posaconazole, voriconazole, proteasome inhibitors, claritromicin, telitromicine) might increase plasmatic concentrations of gefitinib. There are no data about the concomitant treatment with drugs that inhibit CYP2D6.

Plasmatic dose of gefitinib can be reduced when is administered concomitantly with drugs which increase CYP3A4 activity such as: phenytoin, rifampicin, barbiturates or St John's Wort.

Antiacids such as omeprazole can increase the gastric pH and it reduces plasmatic concentrations of gefitinib. Omeprazol and other proton pump inhibitors cannot be used in combination with gefitinib.

Those patients under treatment with warfarin should be monitored as per standard practice because there is an increased risk of hemorrhagic events or INR alteration.

5.7.3 Supportive care in case of toxicity

Please refer to Appendix F.

5.7.4 Other concomitant therapies

In case of RECIST 1.1 progression on a known lesion during osimertinib treatment, surgery, radiotherapy and cryotherapy will be allowed.

No other systemic anticancer therapies will be allowed.

Administration of Covid vaccine will be a treating physician decision after evaluation of benefit-risk ratio and depending of local vaccine availability and compliance with local regulatory guidelines. In cancer patients, the use of inactivated virus vaccines are usually permitted and live vaccines are generally prohibited in those receiving immunosuppressive treatments. Information on the mRNA based COVID-19 vaccines when used in cancer patients is currently not available. See Appendix F for EMA recommendations.

6 Clinical evaluation, laboratory tests and follow-up

As described in chapter 4, a cycle of treatment is defined as 28 days of once daily treatment with osimertinib or gefitinib.

In arm A, after 24 weeks, the duration between study visits will change from every 28 days (4 weeks) to every 56 days (8 weeks).

In arm B and C, study visits will be every 28 days (4 weeks) until the switch to osimertinib. After that, one visit will be performed 28 days after osimertinib initiation, the second one at 8 weeks with radiological evaluation and then every 56 days (8 weeks) if no progression on the first CT scan after osimertinib initiation.

6.1 Arm A

6.1.1 Before randomization

Baseline assessments need to be performed within 21 days prior to randomization:

- Signature of the informed consent;
- Assessment of eligibility criteria;
- Assessment of the baseline signs and symptoms and adverse events based on CTCAE version 4.0, performance status and medical history;
- Collection of concomitant medication;
- Demographics, physical examination, including vital signs, height, weight and blood pressure;
- Laboratory examination including:
 - hematology: white blood cell (WBC) with differential count, platelets (PLTs), hemoglobin (Hb);
 - biochemistry: blood urea nitrogen (BUN), serum creatinine and calculated creatinine clearance (by Cockcroft), uric acid, albumin, total bilirubin, Alkaline Phosphatase (AP), Aspartate AminoTransferase (AST/ASAT), Alanine AminoTransferase (ALT/ALAT), Gamma-Glutamyl Transferase (GGT), sodium, potassium, Lactic Dehydrogenase (LDH), total calcium, phosphorus, magnesium, glucose;

Note: * Electrolyte abnormalities (hypokalemia, hypomagnesaemia, hypocalcemia) must be corrected to be within normal ranges prior to first dose and electrolyte levels monitored during study treatment.

- Beta HCG (serum) for women of childbearing potential. This test must be negative within 72h before first dose of treatment;
- Stick urinalysis;
- Digital ECG with QTc interval; no alteration in QTc interval should be reported before osimertinib initiation:
- LVEF assessed by MUGA or ECHO
- Collection of plasma sample for central T790M status;
- Collection of tumor sample for translational research (please refer to section 10.2);
- Thoracic and upper abdomen contrasted-enhanced CT scan (including adrenal glands) and brain CT scan; if a patient is allergic to contrast adequate premedication as per local practice should be provided. Should there be any further constraint, the EORTC Headquarters should be contacted as soon as possible.
- Ophthalmological examination;
- Geriatric G8 assessment for 70 years old patients or older.

